#### 4.3.4 Economic evaluation

# **Aims and Objectives**

#### **Primary objectives:**

- To estimate the total cost of developing, setting up and running the Y-Check intervention
- To estimate the cost per improvement of well-being from implementing the Y-Check intervention
- To estimate the cost per DALY averted from implementing the Y-Check intervention

#### **Secondary objectives:**

- To estimate the cost of screening for each individual health condition or risk factor
- To estimate the cost per condition detected
- To estimate the cost of providing prevention and promotive advice
- To estimate the cost of providing on the spot healthcare for each health condition
- To estimate the cost of referral for each health condition

A costing study will be conducted to estimate the total costs of developing, setting up, and running the Y-Check package. A combination of top-down and ingredients-based costing approaches will be used to generate cost estimates for the whole package, and for each component/activity. All costs will be estimated from the societal perspective (the adolescents, the schools/community and implementing partners). Financial and economic costs will be calculated for all inputs. Costs will be collected from accounting records, through staff time survey, and process evaluation data including interviews with participants. Capital costs and those costs with a lifespan greater than the project life will be annualised over their useful life. Costs will be inputted into an Excel-based costing tool. The cost analysis will describe the distribution of costs across different forms of inputs, and will estimate the unit cost per adolescent reached, screened, and treated, cost per unit of measure for selected intervention outcomes such as cost per condition detected and cost per condition appropriately treated/referred within 4 months.

A well-being measure developed and adapted during phase 1 will be used to estimate the cost-effectiveness of the intervention measure as cost per improvement in adolescent well-being. Where data are available, we will estimate the cost per DALYs averted.

The cost and cost-effectiveness estimates will be compared to similar programmes in the region and will inform programme replication, scalability, and financial sustainability for different implementing partners.

# 4.4 Knowledge dissemination and translation (Phase 3)

Throughout the study, the Y-Check team will collaborate with MoHCC and MoPSE on the development of the intervention, including development of educational materials and the screening questionnaire. Study teams will provide routine assessment of progress and interpretation and dissemination of the findings to Ministries as well as other key stakeholders including school officials and community leaders. WHO will facilitate policy engagement and dialogue in countries with key country and regional office staff including Y-Check as part of their regular country dialogues with national counterparts.

During the final phase of the project, the study findings will be disseminated to all stakeholders via dissemination meetings and other engagement opportunities. Using the findings of the study, we will develop a set of methodological guidelines for the adaptation, implementation and evaluation of Y-Check in other LMICs settings. We will develop study protocols for additional larger scale implementation and/or rigorous evaluation studies with the aim of providing evidence on the impact of the programme on both educational and health outcomes.

# 5. Data management

# 5.1 Types of primary data

The different forms and uses of data within the study are summarised in Table 3 along with the proposed consent procedures.

# 5.2 Secondary data analysis

We will conduct secondary data analysis of de-identified routine health facility and other service use data to get a better understanding of adolescent's current use of health services. Routine health facility data includes data on screening and testing, and on services received e.g. family planning, HIV care. Data will be aggregated by service setting and we will request a waiver of consent to use the data.

We will conduct secondary data analysis of school register data to understand overall school attendance using aggregated de-identified data for all students in the target age-range/school years. For individual cohort members, we will also review their school attendance and performance records as part of outcome measurement.

# **5.3 Data quality and standards**Data collection

The data collection and entry processes will be as detailed in Standard Operating Procedures. We will use Open Data Kit (ODK) for electronic capture of quantitative data into custom-designed forms with built-in range, consistency and discrepancy checks. Sensitive questions will be input by adolescents themselves to prevent social desirability bias. Tablets will be password protected and personal identifiers will be stored in an encrypted format. Service use will also be captured in paper log books and registers designed for the specific care and prevention services provided. In each case a log will be kept of the number of people reached, products used, tests performed etc. Log books will be entered onto computer on a weekly basis on pre-designed forms.

De-identified field notes, team debrief summaries, and outputs from Participatory Action Research (i.e. pictures from mapping, scoring and ranking activities, photographs from photovoice and pictures drawn

during focus group discussions) will be stored electronically. Audio recordings of discussions and interviews will be transcribed verbatim or summarised in detail and then translated (if applicable) into English for analysis by a fieldworker and stored electronically. Each transcript will also have an accompanying summary form capturing details of the data collection and basic demographic details of the interviewee, as well as any pertinent issues related to the data collection session worth noting. Verbatim quotes may be included in reports or publications, but will only identify the category of participant, their sex and age. De-identified routine health facility data on uptake of health services by adolescents before, during and after the Y-Check implementation period will be collected.

#### Storage and access to data

Data collected off-line on tablets will later be synchronised over our local wi-fi network to the ODK server. Any data transfer over wireless or mobile networks will use Virtual Private Networks or router protected dedicated internet protocol addresses. Data will be fully encrypted to comply with GDPR regulations, using a public and private key for encryption and decryption respectively. All electronic data will be stored in password protected database systems, with access granted to authorised

 Table 3 Primary data collection and consent procedures

Time-point	Data collected	Consent procedure
	Intervention development	
Throughout Year 1	Crowdsourcing contest: Short questionnaires from participants (socio-demographics); contest metrics (number and type of entries etc.); contest entries including images, videos or written documents;	Crowdsourcing contest participants will agree to standard contest terms and conditions including the use of their sociodemographic details and entries.
	Evaluation of crowdsourcing: In-depth interviews with participants and organisers	Contest participants and organisers will provide written informed consent/assent prior to interview. Parent/guardian written consent for 10-15y olds.
	Validation and Intervention design activities: Questionnaire and clinical data from	Client written informed consent/assent.
	validation studies of screening tools. Qualitative data on acceptability of referral pathways.  Findings from the co-creation of the intervention package through participatory workshops with adolescents, the Youth Advisory Group, investigators and stakeholders.	Parent/guardian written consent for Y-Check 1 and Y-Check 2 (schools) only.
	Annonymised meeting/workshop attendance registers (affiliation, sex, age)	
	Y-Check check-up visits (service	es)
Registration	Sex, date of birth.  Contact details (name, phone number, address) linked to ID number recorded in a separate file	Client verbal consent (Y-Check 2 at community hubs)  Parent/guardian written consent
		and participant written assent for Y-Check 1 and Y-Check 2 (school-recruitment) only.
Self-completed questionnaire and provider recorded treatment/counselling services	Age, sex, school/hub, screening test data, screening results, treatments received, and referrals provided for a range of conditions and behaviours.  HIV oral mucosal transudate and STI test results from a maximum of 1100 adolescents aged 16.10 years.	Client verbal consent for use of de- identified data for programme monitoring and improvement purposes. (Y-Check 2 at community hubs)
	adolescents aged 16-19 years.	Parent/guardian written consent and participant written assent for Y-

	Backend digital platform data: information	Check 1 and Y-Check 2 (school-	
	viewed, games played, data from screening apps, rewards provided/used etc.	recruitment).	
Y-CHECK referral &	Referral voucher with ID number, sex, age	Client verbal consent for	
referral service	and reason for referral	information to be shared with	
attendance	Timing of uptake of service within 0-4 months post check-up visit linked to ID	service providers (Y-Check 2 at community hubs)	
		Parent/guardian written consent and participant written assent for Y-	
		Check 1 and Y-Check 2 (school-	
		recruitment).	
Additional	Cost data	None	
programme			
monitoring data			
	Outcomes and evaluation		
Pilot study &	Self-reported questionnaire data	Client written informed consent.	
Cohort study	(demographics, location data, contact	(Y-Check 2 at community hubs)	
	details, study outcomes not captured in		
	programme data including knowledge,	Parent/guardian written consent	
	reported behaviour, well-being and self-	and participant written assent for Y-	
	esteem, acceptability and reported uptake	Check 1 and Y-Check 2 (school-	
	of services)	recruitment).	
Adolescents and	Sociodemographic data, audio-taped	Participant written informed	
stakeholders	interviews, transcripts of IDIs, paired/group	consent.	
(adolescents	interviews and / or FGDs		
providers, family	Process evaluation data on the	Parent/guardian written consent	
members of	implementation, mechanisms of impact and	and participant written assent for Y-	
adolescents,	context of the intervention	Check 1 and Y-Check 2 (school-	
community	Notes from structured / unstructured	recruitment) only.	
members)	observations		
	Annonymised meeting/workshop		
	attendance registers (affiliation, sex, age)		

staff only. When necessary, subsets of the redacted database or other data files may be stored on the PI's or senior staff's laptop to permit analyses during visits or travel. Laptop storage will be encrypted and password protected to protect data from unauthorised access. Data transferred to LSHTM will be held on the LSHTM Secure Server, an NHS-IGT compliant storage system that provides access controls, integrity verification, encryption, automated daily backup and other functionality to ensure data authenticity and security.

## Data management and analysis

The data management team will regularly report on data completeness and quality to the study team throughout the period of data collection. All analyses of the source data will follow standard good

practice, with consistency checks of the final analysis files against the original versions of the data base to ensure numbers of participants, number of events and person-time at risk are consistent after processing of data. Y-Check data will be analysed and stored in accordance with ethical and legal conditions established during that study. Data redaction will be performed to ensure that the files that will be used for analyses in this study do not contain any participant-identifiable or other non-required fields.

## Data documentation, sharing and archiving

New documentation will be written for the purpose of enabling research reproducibility. We will write a codebook including a description of all data collection instruments used. Summary results will be made openly available. Data will be suitable for sharing. The study team will have exclusive use of the data for one year following the end of data collection. The data sharing plan is described in the participant information and consent forms, and participants will be asked for their consent to future sharing. Participants will have the right to exclude their data from further use, as an option on the consent form. If they choose this option, their data will be deleted from the reposited dataset. After study completion, data will be stored in the LSHTM-curated digital repository 'Data Compass' following GDPR guidelines. Data and code registered in LSHTM Data Compass will be made available following deposit. The Biomedical Research and Training Institute has an Information Management and Security policy which ensures that data generated during any study under BRTI will be held with confidentiality and integrity as covered in the ISO15189 standards.

# 6. Statistical considerations and Data analysis

## **6.1 Outcomes**

Outcomes (see Section 4.3.2) will be assessed using:

- Programme data collected during the check-up visit and at the referral services
- Research data collected through the pre-consultation questionnaire, exit interview, and during follow-up visits in the subsequent 12 months.
- School register data for the 12 months before and after Y-Check school visits

The primary outcome will be the proportion of those screening positive for at least one condition who receive appropriate on-the-spot care or complete appropriate referral for all identified conditions within 4 months.

- Completed referral is defined as attending at least the first referral appointment. We expect referral/treatment to have occurred within 4 months.
- Where a client has been diagnosed with more than one condition they must have had completed
  care or referral for each of those conditions in order to be included in the numerator for the
  primary outcome.

Secondary implementation outcomes:

- The proportion of those who screen positive for individual conditions that have had their condition correctly managed within 4 months
- Yield of previously undiagnosed and un-referred conditions
- Intervention acceptability, adoption, appropriateness, feasibility, fidelity and cost (see Process Evaluation Section 4.3.3 for further details)

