In this hybrid effectiveness-implementation study, both data on implementation process, and adolescent outcomes will be captured. A mixed-methods process evaluation will describe the programme implementation, context, and mechanisms of action. The study cohort will be followed up for approximately 12 months with adolescent process and outcome data collected at screening, 4-month and 12-month follow-up visits (**Figure 2**). An economic evaluation will estimate unit costs per adolescent screened, condition identified and case treated, and estimate the cost-effectiveness of the intervention in improving adolescent well-being. Where data are available, we will estimate the impact

of the intervention on DALYs averted. We will gather information to develop methodologies for a potential larger future study to measure the longer-term health, well-being and educational impact of the programme. We will assess the scale up and financial sustainability of the programme.

The prospective intervention study design is more appropriate than a randomised controlled trial (RCT) for answering the research question because i) it is impossible to measure the adolescent outcomes in the absence of the screening which is an integral part of the Y-Check intervention; ii) the intervention components are known to be effective for identifying conditions for which known effective interventions exist (e.g. Provision of spectacles for adolescents with myopia; provision of psychological interventions by trained lay mental health providers through the "Friendship Bench" approach for adolescents with symptoms of significant common mental health disorders), so a control arm in which adolescents were screened, found to have these conditions but not offered care would be unethical; and iii) the great majority of conditions being screened for are chronic, so the prevalence of previously undiagnosed and untreated conditions or risky behaviours provides its own counterfactual reflecting a lack of prior appropriate diagnosis and effective treatment.

COVID-19, which the WHO declared a pandemic on 11 March 2020, has had significant effects on research activities worldwide. Over the past 18 months, adaptations to procedures have allowed research activities to continue in a safe environment for research staff and participants.

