#### Secondary client outcomes:

- Knowledge about health services and health behaviours
- Agency to make decisions about health
- Self-esteem
- Well-being

Knowledge, agency and self-esteem will be measured using questions from existing tools or using new locally-specific questions that will be developed and validated during Phase 1.

The following definition of adolescent well-being has been proposed 'Adolescents thrive and are able to achieve their full potential'.  In Phase 1, the development of a tool to measure wellbeing will build on extensive previous work led by study team member [name] on adapting, developing and testing wellbeing measures for use in economic evaluations of complex interventions in Malawi, Mozambique and Uganda. 

- Reported health-related risk and protective behaviours (see Appendix 1)
- Reported engagement with health services

Reported use of health services will be measured in the past 4 months and in the past 12 months. Use of health services in the past 12 months by 10-24 year olds is proposed as an indicator for monitoring adolescent health worldwide.

- Clinical outcomes (see Appendix 1)
- Educational outcomes

School attendance and attainment in the year prior to and after the initial Y-Check visit will be captured through a review of school registers and/or self-reported by participants during visits. In Phase 1 we will explore the feasibility of measuring cognitive skills and ability, for example through a standardised reading test or computer based tasks of verbal and visuo-spatial working memory.

• Client-centered outcomes (to be defined during Phase 1- see section 2.3)

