## **Prospective Intervention study**

We will follow the STROBE guidelines for the reporting of cohort studies. We will create a flowchart showing the number of communities and schools and the number of participants per community and school at each contact point in the cohort study. We will use descriptive analysis to compare the community-level and school-level characteristics of the four study communities and schools.

The primary outcome is a single proportion which will be presented with a 95% confidence interval for each of the 4 target populations: 10-13y male, 10-13y female, 16-19y male, 16-19y female. Secondary outcomes which are measured at a single time point will be presented in a similar way. For outcomes which are measured at two or more time-points, a before-after analysis will be conducted comparing differences in measures between the two time-points. The unit of analysis will be the individual. For clinical outcomes which are measured at two or more time-points, the initial check-up visit (baseline) will give the prevalence of undiagnosed and untreated chronic conditions which will represent the counterfactual. The proportion of undiagnosed and untreated chronic conditions at the 4-month follow-up visit will be formally compared to this counterfactual to estimate the effectiveness of the intervention in improving these clinical outcomes. We will assess health service and client determinants of correct management of conditions at 4 months using multivariable regression.

**Digital platform data** De-identified data on information viewed, games played, rewards provided/used along with programmatic data on behaviours and clinical conditions etc. will be analysed using machine learning approaches to understand the sub-groups/segments of adolescents who participate in Y-Check. This analysis will help us to define, develop, and pilot test targeted messaging for different sub-groups of young people who attend Y-Check follow-up visits. We will also analyse this data to develop algorithms which could potentially be used in the future phases of the Y-Check programme to further personalise the Y-Check user experience to maximise relevance, uptake and retention.

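### Attendance and attainment are compared before and after with no same-period comparison, although aggregate attendance registers for the same school years are already to be collected

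*Protocol*

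**What the plan says.** Section 6.1 lists "School register data for the 12 months before and after Y-Check school visits" among the outcome sources. It defines the educational outcome as "School attendance and attainment in the year prior to and after the initial Y-Check visit", taken from registers, self-report or both. For outcomes with two or more time-points, section 6.3 states that "a before-after analysis will be conducted comparing differences in measures between the two time-points", with the individual as the unit of analysis.

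Two places explain why no control group is needed. Section 2.3 argues that "the great majority of conditions being screened for are chronic, so the prevalence of previously undiagnosed and untreated conditions", or of risky behaviours, supplies its own counterfactual. Section 6.3 repeats this for clinical outcomes only: the baseline visit gives the "prevalence of undiagnosed and untreated chronic conditions which will represent the counterfactual". Neither place mentions education.

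Section 5.2 plans a separate analysis of school registers "to understand overall school attendance using aggregated de-identified data for all students in the target age-range/school years". It also plans a review of individual cohort members' attendance and performance records as outcome data. No section links the aggregate to the cohort's change.

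On use of the result, objective 2.v in section 2.2 asks for first estimates of the programme's impact on educational outcomes, to help plan a larger study. Section 4.3.2 calls the 12-month education data preliminary.

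**The concern.** Attendance and attainment are not untreated chronic conditions that would stay put without care. Eligible pupils are in Grades 5 to 7 or Forms 3 to 5 (section 4.3.1), and most can be expected to move up a grade between the two windows. General conditions in the schools may also differ from one year to the next. A before-after change in the cohort mixes these influences with any effect of Y-Check and cannot separate them.

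What is at stake is the input to the next study. If the change is carried forward as an early impact estimate, a general rise would make Y-Check look helpful for education, and a general fall could hide a benefit or look like harm. The protocol already plans to collect attendance data that would show much of the general movement, but states no use of them for this purpose.

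**Working it through.** **1. Plan's own figure.** There is none to reproduce. The protocol states no SD, expected change or sample size for attendance or attainment. Steps 3 to 5 therefore rest on assumed inputs.

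**2. What the comparison estimates.** Let τ be the effect on the cohort and δ the general change between the two windows. The expected before-after change is τ + δ, so the bias is δ. Sample size does not enter it.

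**3. Illustration in points.** Assume 700 pupils with register data, τ = 0 and δ = 2 points. With SE = SD/√700 and z = 2/SE:

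| SD of change (assumed) | SE | z |
|---|---|---|
| 10 | 0.38 | 5.3 |
| 15 | 0.57 | 3.5 |
| 20 | 0.76 | 2.6 |

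**4. Illustration in SD units.** With τ = 0 and a general shift of s SDs of individual change, a two-sided 5% test rejects with probability Φ(s√n − 1.96) + Φ(−s√n − 1.96). For s = 0.1 and n = 500, s√n = 2.236, giving Φ(0.276) + Φ(−4.196) ≈ 0.609. The sizes 500 (one sex and age group) and 1000 (one age group) come from section 6.2.

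| s (assumed) | n = 500 | n = 1000 |
|---|---|---|
| 0 | 5.0% | 5.0% |
| 0.05 | 20.1% | 35.3% |
| 0.1 | 60.9% | 88.5% |
| 0.2 | 99.4% | close to 100% |

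**5. Effect of differencing.** In 20,000 simulated studies with τ = 0, n = 500, an unexposed comparison group of equal size, the same trend and independent pupils, the plain test rejected in 4.9%, 60.8% and 99.5% of runs at s = 0, 0.1 and 0.2. The difference in changes rejected in 4.7%, 5.0% and 5.2%. This is an idealised case; few schools and aggregate data would give less precision.

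**6. What the planned registers can deliver.** Let A be the mean attendance change over all N pupils in a school year and C the mean over its n cohort members. The remaining pupils' change is R = (N·A − n·C)/(N − n), so C − R = N(C − A)/(N − n). Leaving cohort members in the aggregate shrinks the contrast by the factor (N − n)/N. If the remaining pupils share δ but gain τc through their own exposure, the expected value of C − R is τ − τc.

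The remainder may be small. Section 3.2 requires at least 200 learners in the primary target year. Section 2.3 plans 1000 participants over 4 to 6 primary schools, that is 1000/4 = 250 to 1000/6 ≈ 167 per school. With six schools, if nearly all participants joined the cohort, a school at the minimum size would keep about 200 − 167 = 33 comparison pupils.

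**The case against.** The other side has several good points.

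- **Claim strength.** A reader might infer that the protocol declares the educational change to be a programme effect. It does not. Section 6.3 reserves formal comparison with a counterfactual for clinical outcomes, section 4.3.2 calls the education data preliminary, and section 4.4 leaves firm evidence on educational impact to later studies. What remains is objective 2.v, which does ask for early impact estimates on education.
- **Pandemic.** A reader might also infer that the protocol describes the year before the visit as disrupted for schools. Section 2.3 speaks of effects on research activities, and its infection-control text concerns delivery of Y-Check. By Figure 2, check-ups run from Q3 2022 to Q2 2023, so only visits made in 2022 have a before-year reaching into 2021. The point needs only grade progression and ordinary year-to-year change.
- **Silence.** Nothing forbids setting the aggregate beside the cohort, and trend handling for a secondary outcome could sit in an analysis plan, which was not available. But the protocol itself fixes the before-after method and the use of the result, so a plan that follows it need not add a comparison.
- **Comparator.** Non-cohort pupils are not untreated. They receive the whole-class sessions (section 3.6), and some may take the full check-up without joining the cohort (section 7.5). They are also self-selected. The planned aggregate covers attendance only, and only the target school years. All of this stands and limits the remedy.
- **Numbers.** The pupil count, SD and drift are assumed, and the z-values ignore clustering within at most 14 schools (8 + 6). Clustering of changes by school would lower z; it would not remove the bias.

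**Conclusion.** The point holds as a cheap improvement to a secondary outcome, for school-recruited participants with register data. The primary outcome is unaffected.

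The before-after comparison has no same-period reference, and the protocol's argument for doing without controls does not cover education. Any general shift therefore enters the educational estimate one for one, whatever the sample size. This follows from the design and needs no assumed figure. How large the shift would be is unknown: the documents give nothing on it, so the z-values and rejection rates show how an uncontrolled test behaves under assumed inputs and are not forecasts.

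The planned registers allow a better comparison for attendance, though a partly exposed and imperfect one. No aggregate comparator is planned for attainment.

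**What to change.** In section 6.3, for register-based attendance:

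1. Report the cohort's before-after change beside, and minus, the change over the same calendar months in the aggregate registers of section 5.2, for the same schools and school years. Subtract cohort members where enough pupils remain. Where registers allow, follow the same class into its next grade; comparing the same grade in successive years would address calendar change but not progression.
2. Use register data on both sides of this contrast, without mixing in self-report, and allow for clustering by school.
3. Label the plain before-after change in attendance and attainment as descriptive, not as programme impact, and word the use under objective 2.v to match.
4. If easily obtained, add aggregate attendance for non-targeted grades in the same schools. This is a small data request beyond section 5.2.
5. State the limits: comparison pupils receive the whole-class sessions, some have had the check-up, and they are self-selected. The difference is probably diluted and not free of confounding.

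The cost is a short amendment and some analysis of data already planned. The registers must be extracted by month and linked to each school's visit date. Attainment stays descriptive unless aggregate performance data are added.
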